PROTOCOL TITLE: Use of a Distal Colonoscope Attachment to Increase Detection of Sessile Serrated Adenomas

1) Protocol Title

Title: Use of a Distal Colonoscope Attachment to Increase Detection of Sessile Serrated Adenomas

Protocol Version Date: *October 29, 2018*

2) Objectives

We plan to compare standard colonoscopy to endocuff-assisted colonoscopy.

Primary Endpoint: Differences in sessile serrated adenoma detection rate (SSADR)

Secondary Endpoints: Differences in:

1. Adenoma Detection Rate
2. Proximal Colon Adenoma Detection Rate

3) Background

Colon cancer remains the second leading cause of death amongst both men and women in the United States.¹ With the advent of screening colonoscopy, mortality from colorectal cancer has decreased, and colonoscopy is the current gold standard for colorectal cancer screening and prevention by removing adenomatous polyps.

Different devices have been employed to assist the endoscopist in the detection of colon adenomas, as these lesions serve as precursors to colon neoplasia. One device of interest is the Endocuff Vision. The Endocuff Vision is a disposable device with a single row of soft, hair-like projections that aid in flattening colonic folds during colonoscope withdrawal to increase the detection of colon adenomas. Previous studies have compared endocuff to standard colonoscopy, and the results have indicated significant improvement in overall adenoma detection rates (ADR).²⁻⁴ All of these studies have focused on the detection of conventional tubular adenomas as primary endpoints. However, there exists an additional serrated adenoma pathway that may give rise to about 15-20% of colon cancers.⁵ These lesions tend to be flatter with subtler features that make them harder to detect. A recent meta-analysis suggested that the endocuff was more effective at detecting sessile serrated adenomas compared to standard colonoscopy; however, these findings are derived from secondary data analyses.⁶ To the best of our knowledge, no study to date has examined the sessile serrated adenoma detection rate as a primary endpoint.

Our previous study examined the differences in overall adenoma detection between endocuff-assisted and standard colonoscopy.⁷ Although there was no statistical difference in ADR between endocuff-assisted colonoscopy and standard colonoscopy, we did observe a numeric difference in sessile serrated adenoma detection rate (SSADR), 16.7% vs 23.8% (p = 0.5) between standard colonoscopy and endocuff-assisted colonoscopy, respectively. Given our previous sample size

PROTOCOL TITLE: Use of a Distal Colonoscope Attachment to Increase Detection of Sessile Serrated Adenomas

was calculated to detect differences in overall ADR, we were not powered to determine whether this observed difference in SSADR was significant.

Therefore, the goal of our study is to compare standard colonoscopy to endocuff-assisted colonoscopy in patients undergoing colonoscopy for colon cancer screening to determine differences in sessile serrated adenoma detection rates.

References:

PROTOCOL TITLE: Use of a Distal Colonoscope Attachment to Increase Detection of Sessile Serrated Adenomas

4) Inclusion and Exclusion Criteria

Inclusion criteria:

(1) Patients between ages of 40 and 85 who are scheduled for screening colonoscopy with the following gastroenterologists at UC Davis :

[name]
[name]
[name]
[name]
[name]
[name] [name]
[name]

Exclusion criteria:

The following patients will be excluded:

- (1) Age less than 40 and greater than 85
- (2) Prior history of colon adenomas (tubular adenoma, sessile serrated adenoma, tubulovillous or villous adenomas) and colon cancer
- (3) Patients with inflammatory bowel disease
- (4) Patients suspected to have colon cancer based on non-invasive tests such as stool tests for hemoglobin or DNA, or imaging finding suggestive of colon cancer (CT or barium enema).
- (5) Patients undergoing colonoscopy for evaluation of symptoms such as abdominal pain, rectal bleeding, diarrhea, constipation, etc., or patient with iron deficiency anemia suspected to be due to ongoing bleeding inside the colon
- (6) Patients with family history of hereditary polyposis syndromes such as Lynch syndrome, familial adenomatous polyposis etc., which are associated with an increased risk of colon cancer
- (7) Patients unable to consent
- (8) Pregnant patients
- (9) Incarcerated patients
- (10) Non-English speaking patients

Number of Subjects:

We plan on recruiting a total of 1374 subjects with 687 subjects randomized to each arm.

PROTOCOL TITLE: Use of a Distal Colonoscope Attachment to Increase Detection of Sessile Serrated Adenomas

Consent Process

Currently, the standard practice is to obtain informed consent prior to a colonoscopy. Some of the patients presenting for their colonoscopy are via open access, thus no colonoscopy specific clinic appointments are done before their actual procedure.

Patients that are identified as being eligible for the study will be contacted 3 weeks prior to their procedure (if possible) but no less than one week. They will be contacted by IRB- approved secured Mychart message via the electronic medical record or telephone by research personnel via IRB approved phone script to inform them of the study. Information regarding the procedure and goal of the study will be provided to allow for sufficient time prior to their procedure to consider participation. A copy of the consent form will also be sent to them via mychart or mail.

Patients agreeing to participate in the study will sign the informed consent form on the day of the scheduled colonoscopy procedure. Patients will be able to ask the consenting physician any questions regarding the study prior to signing the consent form.

As part of routine practice, our endoscopists will discuss with the patients about the colonoscopy - including consent, medication/ history review and discussions about the risks/benefits of the procedure. This conversation typically occurs in a quiet and private section in the pre-op rooms about 30-60 minutes before the procedure. The written consent discussion specific to our study will also be done in this same area. There is usually adequate time prior to the procedure for both the consents to be done.

Please see attached Consent form (HRP-502). Non-English speakers will not be included in the study due to the practical difficulty with translating the study materials and consents. Patients that are unable to provide consent for themselves will not be included in the study.

HIPAA Authorization for Research

With the approval of HIPAA Waiver of Authorization (HRP-441), the study coordinator may identify potential subjects through the Electronic Medical Record (EMR). Following the identification of a patient as a potential subject, the study coordinator may inform the potential subjects of the study via secured communication (MyChart messages) or telephone with an IRB-approved phone script.

5) Study Timelines

Timeline for enrollment of subjects will be November 2018 – May 2020. Data will be obtained from all patient medical records on an ongoing basis and completed once their pathology report is finalized (sessile serrated adenoma vs tubular adenoma vs. non-adenomatous polyps). Primary data analysis will begin immediately once all patients

PROTOCOL TITLE: Use of a Distal Colonoscope Attachment to Increase Detection of Sessile Serrated Adenomas

have been enrolled, completed colonoscopy and all data collected. We anticipate that primary data analysis will be completed by June 2020. This will be a one-time participation during the date of their procedure only. Subjects will only be contacted by their endoscopist for communication of colonoscopy results per regular standard practice at UC Davis.

6) Study Endpoints

Primary Endpoint:

- Sessile Serrated Adenoma Detection Rate

Secondary Endpoints:

- Overall adenoma detection rate
- Proximal colon adenoma detection rate
- Mean number of adenomas per colonoscopy
- Mean number of sessile serrated adenomas per colonoscopy
- Adenomas per positive colonoscopy
- Sessile serrated adenomas per positive colonoscopy
- Colonoscope withdrawal time
- Differences if quality of colon preparation
- Major complication rates (perforation, major bleeding causing transfusion)

7) Procedures Involved

Our proposed study is a randomized control trial in which patients are randomized in a single-blinded fashion into one of 2 study arms. One arm of subjects will undergo their screening colonoscopy without any colonoscope attachments (conventional). A second arm of subjects will undergo their screening colonoscopy with the Endocuff Vision attachment.

All methods (colonoscopy without any attachment and colonoscopy with Endocuff Vision attachment) are approved standard of care options, and are already in clinical use.

Data that will be reviewed as part of the study includes: age, gender, smoking status, alcohol consumption, body mass index (BMI), history of diabetes, quality of bowel prep, withdrawal time, the number of polyps, location of polyps removed, size of the polyps removed, and histopathology of the polyps. These are data points that are routinely collected and reported as part of regular care of patients. This data will be reviewed and entered into the REDCap database by medical students, residents or fellows. GI faculty members' role will be to obtain consent, perform procedures, and analysis of the de-identified data.

8) Data and/or Specimen Management and Confidentiality

Data will be accessed from patient records using an encrypted, password-protected computer at UC Davis Medical Center. The computer is stored in the GI office in PSSB building. This room is accessible by staff/faculty members of the UC Davis Gastroenterology department. Each study patient will be assigned a unique study number. Patient identifier, including patient name (First and Last) and medical record number (MRN) associated with the study number will be entered into password protected REDCap along with other aforementioned data. The principal investigators will not have access to the REDCap database, and research staff responsible for data entry will export de-identified data and distribute de-identified data to the investigators conducting data analysis.

As staff of UC Davis, each investigator will have completed HIPAA compliance training.

The data collected will be analyzed using a one-way ANOVA. Using a baseline incidence of sessile serrated adenoma detection rate of 10%, and to detect an effect size of 50%, with a power of 0.809, we would need 687 subjects in each study arm. We therefore aimed to enroll 687 subjects into each arm (2 arms for a total of 1374 subjects) to ensure we have enough subjects in each arm to detect an effect if present.

9) Data and/or Specimen Banking

Linkage between patient identifiers(First Name, Last Name, and MRN) and study number including other data will be saved on the UC Davis REDcap database using an encrypted, password-protected computer at UC Davis Medical Center, division of Gastroenterology office located at [name] and Ticon I. Only study staff designated for data entry will have access to the REDCap database. Upon request, the de-identified data will be exported from the REDCap database and distributed to the investigators for analysis. De-identified data used for this study will not be banked for future use. At the completion of the study, all linkage between the patient identifiers and the study number will be destroyed.

10) Provisions to Monitor the Data to Ensure the Safety of Subjects

This research does not involve more than minimal risk to the subject.

The PI affirms to uphold the principle of the subject's right to protection against invasion of privacy. Throughout this study, a subject's source data will only be linked to the study database or documentation via a unique identification number. As permitted by all applicable laws and regulations, limited subject attributes, such as sex, age, or date of birth, and subject initials may be used to verify the subject and accuracy of subject's unique identification number.

11) Withdrawal of Subjects

Participation in the study is completely voluntary, thus patients can withdraw at any time during or after the procedure. Written consent will be obtained from all subjects.

Withdrawning from the procedure has no negative implication on their colon cancer screening and subsequent clinical care. If a subject desires to withdraw from the study, all information associated with the particular subject will be discarded immediately.

A patient may also be withdrawn from the research at the discretion of the endoscopist or PI. The PI may withdraw a subject if there is a clinical suspicion for hereditary polyposis syndrome and/or new case of inflammatory bowel disease (IBD) based on the colonoscopy. Also, there are scenarios where the regular colonoscope is switched to a pediatric colonoscope. This occurs in patients with altered/ post-surgical anatomy, preventing completion of the procedure using a standard colonoscope. In these cases, subjects may be withdrawn from the study.

12) Risks to Subjects

The attachment device proposed in our study is currently FDA approved for use in colonoscopy. There is no added risk to participating subjects. There is an overall minimal risk to subjects and that risk is similar to any and all risks for conventional colonoscopy. Although we will make every effort to ensure that all patient health information remains confidential, there is the risk of loss of confidentiality.

PROTOCOL TITLE: Use of a Distal Colonoscope Attachment to Increase Detection of Sessile Serrated Adenomas

13) Potential Benefits to Subjects

Subjects may benefit from increased sessile serrated adenoma detection.

14) Multi-Site Research

Only UC Davis Medical Center Endoscopy suites will be involved in this study.

15) Community-Based Participatory Research

Not applicable

16) Sharing of Results with Subjects

Under current standard of practice, patients are contacted by the endoscopist either through the phone, mail, my chart or in person during a clinic visit to discuss endoscopic and pathology results. The results of the study will not be shared with subjects until the study has been completed and all of the data has been analyzed.

17) Prior Approvals

Not applicable

18) Provisions to Protect the Privacy Interests of Subjects

The only people that will have access to subject personal information are the principal investigators, sub-investigators and research personnel during the study period. All information collected (including age, gender, smoking status, alcohol consumption, BMI, diabetes status, withdrawal time, bowel prep quality, size, number and types of polyps removed, cecum intubation time and complications of procedure) will be de-identified.

19) Compensation for Research-Related Injury

No compensation will be provided.

20) Economic Burden to Subjects

Patients presenting for colonoscopies are typically insured and are not expected to pay for screening colonoscopies. The study will not provide or pay for the endocuff since it is already approved for use at each study site as standard practice. The endocuff is an additional tool to detect polyps at the discretion of the endoscopist. There is no additional billing code when this device is used, and it is included in the standard screening colonoscopy visit. Therefore, there is no expectation that patients who are randomized to

PROTOCOL TITLE: Use of a Distal Colonoscope Attachment to Increase Detection of Sessile Serrated Adenomas

the endocuff arm will incur additional costs versus those that are randomized to colonoscopy without endocuff.

21) Drugs or Devices

The Endocuff Vision device being used is FDA approved for use during colonoscopy. No investigational devices are being used in this study.

22) [ClinicalTrials.gov](#) Registration

FDAAA 801 establishes penalties for Responsible Parties who fail to comply with ClinicalTrials.gov registration or results submission requirements. Penalties include civil monetary penalties and, for federally funded studies, the withholding of grant funds.

For additional information on registration and results submissions requirements click [here](#).

If registration is necessary the following are required:

- *Registration and, in some instances, submission of results at Clinicaltrials.gov*
- *Specific clinicaltrials.gov language in the consent form for this research. The language can be found in HRP 502 Template Consent under the heading "What happens to the information collected for the research?"*

Complete each section below. If you finish a section indicating the research must be registered on Clinicaltrials.gov is required you do not have to complete the remaining sections.

Section 1: NIH Funded Studies

If yes to BOTH, the study must be registered on Clinicaltrials.gov.

Yes	
	This study is funded by the NIH . (If this study is not funded by NIH, go to Section 2.)
	One or more human subjects will be prospectively assigned to one or more interventions (which may include placebo or other control) to evaluate the effects of those interventions on health-related biomedical or behavioral outcomes.

Section 2: Studies subject to FDA jurisdiction

If yes to ANY the study must be registered on Clinicaltrials.gov.

Yes	
	This is a prospective clinical study of health outcomes in human subjects that

PROTOCOL TITLE: Use of a Distal Colonoscope Attachment to Increase Detection of Sessile Serrated Adenomas

	compares an intervention with an FDA-regulated device against a control. This is not a small clinical trial to determine the feasibility of a device, or a clinical trial to test prototype devices where the primary outcome measure relates to feasibility and not to health outcomes.
	This is a pediatric post market surveillance of a device as required under section 522 of the Federal Food, Drug, and Cosmetic Act.
	This is a controlled clinical investigation, other than a phase I clinical investigation, of a drug subject to section 505 of the Federal Food, Drug, and Cosmetic Act or to section 351 of the Public Health Service Act.

To view a flowchart describing applicable clinical trials subject to FDA jurisdiction click [here](#).

Section 3: Publishing the results

If yes to BOTH the study must be registered on Clinicaltrials.gov.

Yes	
	This study prospectively assigns people or a group of people to an intervention, with or without concurrent comparison or control groups, to study the cause-and-effect relationship between a health-related intervention and a health outcome.
	The PI has access to and control over all the data from the clinical trial and has the right to publish the results of the trial and plans to publish the results in a journal that follows the ICMJE recommendations .

This requirement includes studies of behavioral interventions.

Section 4: Registration on Clinicaltrials.gov is not required

Yes	
	I have read sections 1-3 above and registration on clinicaltrials.gov is not required for this research.

23) Criteria for 10 Year Approval

If yes to all items below this research may qualify for a 10-year approval period.

Yes	
	This research involves no more than minimal risk.
	This research does not receive any federal or state government funding or funding from a private funder who requires annual review per contract.
	This research is not subject to FDA jurisdiction.
	This research does not include prisoners as participants.
	This research is not subject to SCRO oversight.
	This research is not subject to oversight by the Research Advisory Panel of California (RAP of C).
	This research does not involve identifiable information held by the State of

PROTOCOL TITLE: Use of a Distal Colonoscope Attachment to Increase Detection of Sessile Serrated Adenomas

	California Department or Agency
	No personnel involved in the design, conduct, or reporting of this research have a new unreported related financial interest (RFI) in this study.

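### The two 'per positive colonoscopy' endpoints should be labelled descriptive: a test among positives only is not a randomised comparison, yet Section 8's blanket ANOVA sentence, read literally, covers both

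*Protocol*

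**What the plan says.** Section 6 (Study Endpoints) lists two secondary endpoints with a restricted denominator: "Adenomas per positive colonoscopy" and "Sessile serrated adenomas per positive colonoscopy". They stand beside "Mean number of adenomas per colonoscopy" and "Mean number of sessile serrated adenomas per colonoscopy", which use every patient. Nothing marks the restricted pair as descriptive, and positive is not defined.

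The only stated method of analysis is in Section 8 (Data and/or Specimen Management and Confidentiality): "The data collected will be analyzed using a one-way ANOVA". It names no endpoint. The sample-size statement follows directly and uses a "baseline incidence of sessile serrated adenoma detection rate of 10%, and to detect an effect size of 50" per cent, with 687 subjects per arm.

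Section 3 (Background) says the device's projections "aid in flattening colonic folds during colonoscope withdrawal to increase the detection of colon adenomas". Section 2 (Objectives), under "Secondary Endpoints: Differences in", names only the overall and the proximal adenoma detection rate.

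**The concern.** Randomisation makes the two full arms comparable. It does not do so for the patients in each arm who turn out positive, once the device affects who is positive. Under a strict null of no effect on detection the positives-only test would be valid. It loses that protection in exactly the situation the trial is sized for, where the Endocuff positives include patients who would have been negative under standard colonoscopy. If those patients tend to carry few lesions, they pull the Endocuff mean down.

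A reader could then be shown no difference, or a significant deficit, for a device that found more lesions and missed none.

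**Working it through.** **The plan's own figure.** The 50% effect is read as relative, so 10% versus 15%. Alpha is not stated; two-sided 0.05 is assumed. The usual formula is n = [1.96·√(2·p̄·q̄) + z(power)·√(p₁q₁ + p₂q₂)]² / (p₂ − p₁)², with p̄ = 0.125.

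- Power 0.80: n = (1.96·0.4677 + 0.8416·0.4664)² / 0.0025 = 686 per arm.
- Power 0.809: n = 702 per arm.
- Power at 687 per arm: 0.801.

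This is close enough to 687 and 0.809 to support the relative reading.

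**Who enters the SSA test.** Positive is taken as at least one SSA. Control: 687 × 0.10 = 68.7, about 69. Endocuff: 687 × 0.15 = 103.05, about 103. If the device misses nothing that standard colonoscopy finds, 0.05/0.15, or one third, of the Endocuff positives are newly positive.

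**Identity (needs no assumed counts).** Mean per positive = mean per colonoscopy ÷ detection rate. If both rise, the ratio can move either way or not at all.

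**When it falls.** Let m₀ be SSAs per positive control patient, n SSAs per newly positive patient, and e the extra SSAs found in each already-positive patient. Then:

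Endocuff mean per positive = [0.10(m₀ + e) + 0.05n] / 0.15 = [2(m₀ + e) + n] / 3

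This is below m₀ when 2e + n < m₀. At break-even, 2e + n = m₀, the per-positive mean does not move, while SSAs per colonoscopy rise by 0.15m₀/0.10m₀ = 1.5. For example, they go from 0.12 to 0.18, 0.15 to 0.225, or 0.20 to 0.30.

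**If every lesion becomes more detectable.**

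- Poisson: −ln(0.90)/0.10 = 1.05 and −ln(0.85)/0.15 = 1.08 per positive.
- Negative binomial, k = 0.5: μ = 0.5[(1 − p)⁻² − 1] = 0.1173 and 0.1920, so 1.17 and 1.28 per positive. Here the mean rises.

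**Illustrative simulation.** 10,000 trials per scenario, 687 per arm, two-group ANOVA at two-sided 0.05. Already-positive counts are 1 + Poisson(m₀ − 1), plus Poisson(e) with Endocuff; newly positive counts are 1 + Poisson(n − 1). The values of m₀, n and e are assumptions.

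| Case | m₀, n, e | Mean per positive, control → Endocuff | Per-positive test: Endocuff lower / higher, % of trials | Per-colonoscopy test: Endocuff higher, % |
|---|---|---|---|---|
| Worst | 1.2, 1, 0 | 1.20 → 1.13 | 18.6 / 0.1 | 63 |
| Worst | 1.5, 1, 0 | 1.50 → 1.33 | 36.9 / 0.0 | 44 |
| Worst | 2, 1, 0 | 2.00 → 1.67 | 59.1 / 0.0 | 27 |
| Milder | 1.5, 1.2, 0.1 | 1.50 → 1.47 | 4.7 / 1.0 | 66 |
| Milder | 1.2, 1.1, 0 | 1.20 → 1.17 | 7.5 / 0.6 | 68 |
| Milder | 1.5, 1.25, 0 | 1.50 → 1.42 | 12.5 / 0.3 | 58 |
| Milder | 1.5, 1, 0.1 | 1.50 → 1.40 | 15.7 / 0.2 | 55 |
| Milder | 2, 1, 0.25 | 2.00 → 1.83 | 17.2 / 0.1 | 48 |
| Milder | 2, 1.5, 0 | 2.00 → 1.83 | 19.6 / 0.2 | 50 |
| Break-even | 1.2, 1, 0.1 | 1.20 → 1.20 | 2.6 / 1.9 | 74 |
| Break-even | 1.5, 1, 0.25 | 1.50 → 1.50 | 2.5 / 1.7 | 71 |
| Break-even | 2, 1, 0.5 | 2.00 → 2.00 | 2.1 / 1.9 | 67 |
| Break-even | 2, 1.5, 0.25 | 2.00 → 2.00 | 2.4 / 2.1 | 69 |
| All lesions | Poisson | 1.05 → 1.08 | 0.45 / 8.0 | 83 |
| All lesions | Neg. binomial, k = 0.5 | 1.17 → 1.28 | 0.05 / 21.0 | 87 |

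The per-colonoscopy test was significantly against Endocuff in 0.02% of trials or fewer in every scenario.

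The protocol gives no adenoma detection rate, so no figure is offered for adenomas; the same identity applies.

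**The case against.** The strongest reply is that the protocol never commits to testing these two means. Section 6 only lists them, Section 2 omits them from the secondary differences, and the ANOVA sentence sits next to the primary sample-size calculation, so it may be meant for the primary endpoint alone. Taken at its word, that sentence would also cover complications, bowel preparation and smoking status, which suggests loose drafting more than a plan. An SAP that is not shown may settle both the definition of positive and the status of these endpoints. This is fair and keeps the point minor. It does not remove it: the one method the protocol states has no limit on its scope, and the two endpoints carry no descriptive label.

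The size of the problem also depends on the model. The worst case requires newly positive patients to have exactly one SSA each and no extra lesion to be found in anyone already positive. That fits poorly with a fold-flattening device, which should act in every patient. When all lesions become more detectable, the wrong direction almost disappears and what remains is low power. This stands, and it is why the 59% figure is an extreme and not an expectation.

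If positive means any adenoma or SSA, the 69 versus 103 and the SSA simulations no longer apply, but the denominator is still a post-randomisation result. Finally, a lower mean among positives is a true property of that quantity, not a false positive; the error lies in reading it as the device's effect. The per-colonoscopy means in the same list would help a careful reader avoid this.

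**Conclusion.** The concern holds as a minor point. The firm part is structural: a positives-only comparison is not randomised once the device changes detection, and by the identity its direction is not a reliable guide to device effect. How often a trial would mislead depends on assumed lesion counts, on 50% being relative, on two-sided 0.05, and on positive meaning at least one SSA. The (m₀, n, e) scenarios also assume the device misses nothing that standard colonoscopy finds. Across all the scenarios, a significant result against Endocuff ranges from almost never to about 59%. In each of them the per-positive test was less likely than the per-colonoscopy test to show the gain, by a wide margin. The primary endpoint and the sample size are unaffected.

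**What to change.** Add one sentence to Section 6 or Section 8 that does three things:

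- defines positive for each endpoint (at least one adenoma; at least one SSA);
- says the two per-positive means are reported descriptively by arm, with no test and no claim of effect;
- says inference on lesion counts rests on the mean adenomas and mean SSAs per colonoscopy in all randomised subjects, which are already listed.

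Data collection, sample size and the primary endpoint do not change. The cost is that two conventional metrics lose their p-values.

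### The trial runs through a fixed list of seven or eight endoscopists, but the protocol makes no provision to balance, adjust for or examine operator differences in SSADR

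*Protocol*

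**What the plan says.** Protocol Section 4 limits eligibility to patients "who are scheduled for screening colonoscopy with the following gastroenterologists at UC Davis", followed by a list of names. The names are removed from the public copy; the placeholders suggest seven or eight endoscopists.

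Section 7 gives the allocation in one phrase: "patients are randomized in a single-blinded fashion into one of 2 study arms". It states no stratification factor, blocking or method.

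Two places list the study data. Section 7 begins "Data that will be reviewed as part of the study includes: age, gender, smoking status, alcohol consumption, body mass index (BMI), history of diabetes" and goes on to bowel preparation, withdrawal time and polyp details. Section 18 gives a similar list ending "size, number and types of polyps removed, cecum intubation time and complications of procedure". Neither names the endoscopist.

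Section 8 fixes the analysis: "The data collected will be analyzed using a one-way ANOVA". It also says that analysts receive a de-identified export from REDCap. Section 9 says that the link between patient identifiers and study numbers is destroyed when the study is complete.

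**The concern.** SSADR depends on who is looking. Section 3 describes serrated lesions as flat, subtle and hard to detect. The operator also delivers the intervention and cannot be blinded to an attachment on the colonoscope. By making a closed list of operators part of eligibility, the protocol itself makes the operator a structural feature of the design.

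The operator then disappears from the plan: there is no stratum, no named data item and no term in the analysis. Operator mix between arms is left to chance, a known source of outcome variation goes unused in the primary test, and no look is planned at whether detection, or the device effect, varies between operators. For a single-centre device trial with so few operators, that weakens the reading of either a positive or a null result. Once the linkage is destroyed, recovering the operator would be difficult.

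**Working it through.** **Inputs from the protocol.** 687 patients per arm, 1374 in total (Sections 4 and 8); stated power 0.809 (Section 8). Section 8 gives the control rate: "Using a baseline incidence of sessile serrated adenoma detection rate of 10" per cent. The effect size of 50% is in the same section.

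**Assumptions.** The 50% is read as relative, so 10% versus 15%. Alpha is not stated; two-sided 0.05 is used. Eight operators of equal volume. Operator-specific SSADRs are not given, so a range is tried.

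**1. The plan's own figure.** Two-proportion formula with pooled null variance (mean rate 0.125):

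z = [0.05 × √687 − 1.96 × √(2 × 0.125 × 0.875)] / √(0.10 × 0.90 + 0.15 × 0.85)
= (1.3105 − 0.9167) / 0.4664 = 0.844, power 0.801.

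This is within a point of 0.809. The same formula gives 686 per arm at power 0.80 and 702 at 0.809. The sample size is reproduced closely enough and is not in question here.

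**2. Chance imbalance in operator mix.** SE of the SSADR difference = √[(0.09 + 0.1275)/687] = 1.78 percentage points (variance 3.166 pp²). Under unstratified 1:1 allocation, the SD of the between-arm difference in mean operator rate is √(2 × Var(rate)/687).

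| Assumed operator SSADRs (8 operators) | Mean | Var (pp²) | SD of imbalance (pp) | 95% range (pp) | Share of variance |
|---|---|---|---|---|---|
| 5–15%, evenly spaced | 10% | 10.71 | 0.18 | ±0.35 | 1.0% |
| 3–17%, evenly spaced | 10% | 21.00 | 0.25 | ±0.48 | 1.9% |
| 2–22%, uneven: 2, 5, 6, 8, 9, 11, 17, 22 | 10% | 38.00 | 0.33 | ±0.65 | 3.5% |

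The third set is spaced unevenly so that it averages 10%. Even spacing over 2–22% averages 12% and gives 0.35 pp, or 3.9% of the same variance. These amounts are already contained in the 1.78-point SE; they are not an extra error on top of it. The target difference is 5 points.

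**3. Effect on the test.** Simulation with 2000 runs per scenario: 1374 patients over 8 operators, randomised 687:687 without stratification, with a common device effect on the logit scale. An unadjusted two-proportion test is compared with a Cochran-Mantel-Haenszel (CMH) test stratified by operator. For scale, one SD either side of a 10% operator is about 6% to 15% at logit SD 0.5, and about 4% to 23% at SD 1.0.

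| Operator SD (logit) | Null rejection: unadjusted / CMH | Power: unadjusted / CMH |
|---|---|---|
| 0 | 0.056 / 0.058 | 0.808 / 0.809 |
| 0.5 | 0.046 / 0.045 | 0.802 / 0.811 |
| 1.0 | 0.056 / 0.054 | 0.803 / 0.840 |

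Simulation error (one SE) is about 0.5 points for the null rates, √(0.05 × 0.95/2000), and 0.9 points for power, √(0.8 × 0.2/2000). The null rates are consistent with 5% for both tests. The gain in power is about 0 to 4 points.

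**4. What by-operator results could show.** 1374/8 ≈ 172 patients per operator, about 86 per arm. The SE of one operator's difference is √(0.2175/86) = 5.0 points, a 95% half-width of about 10 points around a 5-point effect. With seven operators (about 98 per arm) it is about 9 points.

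**The case against.** The strongest objection is that this is silence, not error. Both data lists are open-ended and plainly incomplete. Neither names the randomised arm, which must be recorded. Section 7 omits complications, although the major complication rate is a secondary endpoint. Section 18 omits polyp location, which the proximal adenoma endpoint needs. A reader might infer that the endoscopist goes unrecorded, so that operator differences cannot be balanced, adjusted for or examined. The documents do not support that. Absence from these lists does not show absence from the database, the operator could be taken from the medical record while the linkage exists, and the protocol does not exclude stratification. This part of the objection stands.

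A reader might also infer that the result would be biased. It would not: randomisation balances operators in expectation, and the calculations show no type I error inflation and a small effect on precision. That stands too, as does the point that within-operator estimates would be too imprecise to show that an effect comes from one or two endoscopists.

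Finally, covariate adjustment may sit in an analysis plan that is not shown. This answers only part of the point. The protocol is not silent on analysis; it fixes a one-factor method. Stratification and data capture are design matters that have to be settled before patients are randomised. Section 8 describes the REDCap content by referring back to the items already listed, so nothing written ensures that an operator code reaches the analysts.

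**Conclusion.** The point holds as a design weakness that should be corrected, not as a threat to validity. The protocol restricts the trial to a closed set of unblinded operators who determine the primary endpoint, and then makes no provision for them in allocation, named data or analysis.

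The size is modest: about 1% to 3.5% of the variance of the primary comparison, and about 0 to 4 points of power. Both figures rest on assumed operator spreads, equal operator volumes, eight operators and two-sided 5% testing; the power figures also assume a common device effect. The rest of the loss is interpretive, since no look at operator variation is planned. The sample size of 687 per arm is unaffected.

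**What to change.** 1. Add a coded item for the endoscopist who performed the procedure to the data lists in Sections 7 and 18 and to the de-identified export, and fill it before the linkage is destroyed. This is the essential step.
2. In Section 7, stratify randomisation by endoscopist, using permuted blocks of varying size, since unblocked allocation within strata would not secure balance.
3. In Section 8, replace the one-way ANOVA for SSADR with an endoscopist-stratified comparison, such as a Cochran-Mantel-Haenszel test or logistic regression with arm and endoscopist.
4. Report SSADR by arm within endoscopist as description only, with intervals, given half-widths of about 10 points.

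Cost: one REDCap field, a stratified allocation list and slightly more set-up. Low-volume endoscopists will form small strata, which can be pooled under a rule set in advance. No extra patients or procedures are needed.
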